8.7.3.2. Self-controlled risk interval design

Sensitivity analyses incorporating a SCRI design will be implemented for outcomes with an acute onset and short risk intervals (i.e., risk intervals no longer than 42 days; specific outcomes to be indicated in the SAP) in the overall study population, in pregnant women, in immunocompromised individuals, and in individuals with a history of COVID-19. The SCRI design will not be considered for pregnancy safety outcomes. Only vaccinated individuals will be included in the SCRI analysis; the rate of a specific safety event in a post-vaccination risk interval will be compared with that in a control interval within the same individual.

For the primary series analysis, the risk interval will combine person-time in the risk intervals after the first dose, after the second dose, and after the third dose (if applicable).

PFIZER CONFIDENTIAL CT24-WI-GL02-RF02 3.0 Non-Interventional Study Protocol Template For Secondary Data Collection Study 20-May-2021 Page 96 of 120 The control interval will be outcome specific, with the duration and timing relative to vaccination specified in more detail in the SAP. Control intervals will be defined during specific periods following vaccination (up to a maximum of 183 days); to avoid bias due to healthy vaccinee effects, pre-vaccination periods will not be used. A washout period between the risk and control intervals may be incorporated for safety events for which the risk interval is not well characterized.

Because of the self-controlled nature of the design, bias of comparative risk estimates arising from differences in the distribution of time-constant confounding factors between vaccinated and unvaccinated individuals is avoided with the SCRI design. Furthermore, as the design only includes vaccinated individuals, it avoids the potential for misclassification of unexposed status due to incomplete capture of COVID-19 vaccinations in data from claims or electronic health records.

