A main limitation of the cohort design with concurrent unexposed comparators is that it may be subject to misclassification of unexposed status, since many vaccinations occurring outside traditional medical care settings without health insurance reimbursement (e.g., mass vaccination campaigns by public health officials) may not be captured in administrative claims data. To address this limitation, sensitivity analysis will incorporate a self-controlled risk interval (SCRI) design for events with an acute onset and a short risk interval (Baker et al., 2015) (defined for the purposes of this study as ≤ 42 days after vaccination). If exposure information is deemed incomplete based on feasibility analysis during the monitoring phase,

PFIZER CONFIDENTIAL

CT24-WI-GL02-RF02 3.0 Non-Interventional Study Protocol Template For Secondary Data Collection Study 20-May-2021 Page 47 of 120 the primary study design may be switched to the SCRI design or linkage with data from immunization registries may be conducted (if feasible). Another limitation of the proposed approach is that outcomes may be misclassified in data from claims and electronic health records. To address this limitation, algorithms for select outcomes that may be susceptible to substantial misclassification may be validated through medical records or review of patient profiles (i.e., chronological listing of a patient's codes in data from claims and/or electronic health records) (see Section 8.3.2.2). The determination of which outcomes may be susceptible to substantial misclassification will be informed by clinical expert opinion and review of validation studies if available.

The study observation period will start on the date that Pfizer-BioNTech original monovalent COVID-19 Vaccine was granted EUA in the US (11 December 2020) and will end a minimum of 3 years after this date. Although only exposures identified through 18 April 2023 (the date that authorization of Pfizer-BioNTech original monovalent COVID-19 Vaccine ended) will be included in the study, outcomes occurring in the predefined risk period will be assessed after this date. The study will include both vaccinations received under the EUA and under the biologic license application (BLA).

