			2,500,000	1.00	1.00	1.00	1.00	
			5,000,000	1.00	1.00	1.00	1.00	
			10,000,000	1.00	1.00	1.00	1.00	
			20,000,000	1.00	1.00	1.00	1.00	
1.4	Myocarditis/ pericarditis		500,000	0.03	0.04	0.05	0.06	
			1,000,000	0.03	0.05	0.07	0.09	
			2,500,000	0.03	0.07	0.11	0.17	
			5,000,000	0.03	0.10	0.18	0.29	
			10,000,000	0.04	0.15	0.32	0.51	
			20,000,000	0.04	0.26	0.57	0.80	

PFIZER CONFIDENTIAL CT24-WI-GL02-RF02 3.0 Non-Interventional Study Protocol Template For Secondary Data Collection Study 20-May-2021

Page 84 of 120

Assumed true RR	Safety event of interest	Estimated back- ground rate per 100,000 person- years (Black et al., 2021; Gubernot et al., 2021)	Number of individuals vaccinated	Probability that the upper confidence limit of RR will be below the following thresholds ^a :				
				1.5	2.0	2.5	3.0	
1.4	Myocarditis/ pericarditis	10	500,000	0.03	0.10	0.18	0.29	
	1		1,000,000	0.04	0.15	0.32	0.51	
			2,500,000	0.05	0.31	0.66	0.88	
			5,000,000	0.06	0.54	0.92	0.99	
			10,000,000	0.08	0.83	1.00	1.00	
			20,000,000	0.12	0.99	1.00	1.00	
1.4	Guillain- Barré syndrome		500,000	0.03	0.06	0.09	0.12	
			1,000,000	0.03	0.08	0.14	0.21	
			2,500,000	0.04	0.13	0.28	0.44	
			5,000,000	0.04	0.22	0.49	0.73	
			10,000,000	0.05	0.40	0.79	0.95	
			20,000,000	0.07	0.67	0.97	1.00	
1.4	Bell's palsy	Bell's palsy 25.2	500,000	0.05	0.31	0.66	0.88	
			1,000,000	0.06	0.55	0.92	0.99	
			2,500,000	0.09	0.91	1.00	1.00	
			5,000,000	0.14	1.00	1.00	1.00	
			10,000,000	0.24	1.00	1.00	1.00	
			20,000,000	0.43	1.00	1.00	1.00	

PFIZER CONFIDENTIAL

CT24-WI-GL02-RF02 3.0 Non-Interventional Study Protocol Template For Secondary Data Collection Study 20-May-2021

Assumed true RR	Safety event of interest	Estimated back- ground rate per	individuals vaccinated of RR will be thr 1.5 2.0	Probability that the upper confidence limit of RR will be below the following thresholds ^a :				
		100,000 person- years (Black et al., 2021; Gubernot et al., 2021)		2.0	2.5	3.0		
1.4	Myocardial 208 infarction		500,000	0.10	0.93	1.00	1.00	
			1,000,000	0.15	1.00	1.00	1.00	
			2,500,000	0.32	1.00	1.00	1.00	
			5,000,000	0.56	1.00	1.00	1.00	
			10,000,000	0.85	1.00	1.00	1.00	
			20,000,000	0.99	1.00	1.00	1.00	

RR = relative risk.

a. Estimates in this table assume a risk window duration of 21 days for myocarditis/pericarditis, 42 days for Guillain-Barré syndrome and Bell's palsy, and 28 days for myocardial infarction.

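### The primary-series SCRI adds up risk time over the doses received, so an event that stops dose 2 shortens risk time only for risk-interval cases and pushes the null RR modestly above 1

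*Protocol*

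**What the plan says.** Protocol section 8.7.3.2 sets out the SCRI. On the population: "Only vaccinated individuals will be included in the SCRI analysis". No completed series is required. On the contrast: the event rate in the post-vaccination risk interval "will be compared with that in a control interval within the same individual". On the primary series: "the risk interval will combine person-time in the risk intervals after the first dose, after the second dose", and the third where it applies. On the control: "The control interval will be outcome specific, with the duration and timing relative to vaccination specified in more detail in the SAP". Control time is post-vaccination only and lies within 183 days. The section claims protection against time-constant confounding and against misclassified unexposed status. It does not discuss an event changing whether the next dose is received.

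Section 8.7.2.2 treats the cohort analysis differently: relative risks are estimated by dose first and combined only if they are similar. Section 8.7.3.2 has no such step.

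Sections 8.7.3.1 and 8.7.3.2 make the SCRI a sensitivity analysis for exposure misclassification. Section 8.1 adds that if exposure data prove incomplete "the primary study design may be switched to the SCRI design", and sections 8.3.1 and 8.9 repeat the option.

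**The concern.** A within-person comparison assumes that the event does not alter how much risk and control time a person has. Summing risk time over doses received breaks this if the event can stop the next dose. A case in the dose 1 window who then skips dose 2 has one window of risk time, and that event always counts as a risk-interval event. A control-interval case has already passed the time of dose 2, so this event cannot have stopped it. The shortened denominators fall only on risk-interval cases, which raises the estimated RR.

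The stake is interpretation. If the cohort and SCRI estimates differ, the SCRI is meant to show whether missed vaccinations explain the difference. A bias built into the SCRI would blur that reading. If the SCRI became primary, the bias would enter the main result.

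**Working it through.** **Inputs from the protocol.** Risk windows of 21 days (myocarditis/pericarditis), 28 days (myocardial infarction) and 42 days (Bell's palsy): Table 8 and the Table 9 footnote ("Estimates in this table assume a risk window duration of 21 days for myocarditis/pericarditis"). Two doses 3 weeks apart: section 6. Background rates and 5,000,000 vaccinated: section 8.5.

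**Assumptions.** Constant event rate. The dose 1 window ends at dose 2 (section 8.7.2.2 states this for the cohort; it is assumed for the SCRI). Control length *c* is the same for everyone. A share *q* of cases occurring before dose 2 skip it because of the event. The protocol gives neither *q* nor *c*, so both are shown as ranges.

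**The plan's own figure.** The protocol gives no precision figure for the SCRI. The cohort figure of 92% confirms how the inputs are used:
- Expected comparator events: 5,000,000 × 2 doses × 10/100,000 × 21/365.25 = 57.5. Expected exposed events: 1.4 × 57.5 = 80.5.
- SE(log RR) = √(1/57.5 + 1/80.5) = 0.173.
- P(upper limit < 2.5) = Φ(ln(2.5/1.4)/0.173 − 1.96) = 0.919.

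This reproduces 92%. With one dose per person the result would be 0.661, so Table 9 counts two doses each.

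**SCRI estimate under a true RR of 1.** Each case with risk time *r* and control time *c* contributes θr/(θr + c) to the score. The estimate solves Σ θr/(θr + c) = number of risk-interval cases.

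Worked case: 21-day windows, *c* = 42, *q* = 1. Cases occur in the ratio 21 (dose 1) : 21 (dose 2) : 42 (control). The 21 dose 1 cases have r = 21, and the other 63 have r = 42:

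21θ/(θ + 2) + 63θ/(θ + 1) = 42, so θ = 1.19.

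At *q* = 0.5: 10.5θ/(θ + 2) + 73.5θ/(θ + 1) = 42, so θ = 1.09.

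| Window | Control (days) | q = 10% | 25% | 50% | 100% |
|---|---|---|---|---|---|
| 21 | 21 | 1.03 | 1.06 | 1.13 | 1.28 |
| 21 | 42 | 1.02 | 1.04 | 1.09 | 1.19 |
| 21 | 120 | 1.01 | 1.02 | 1.04 | 1.08 |
| 28 | 49 (= full risk time) | 1.01 | 1.03 | 1.06 | 1.13 |
| 42 | 63 (= full risk time) | 1.01 | 1.02 | 1.03 | 1.07 |

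With 21-day windows and a 42-day control, a true RR of 1.4 reads as 1.47, 1.55 and 1.72 at *q* = 25%, 50% and 100%.

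**False-signal rate** (simulated; nominal 2.5% for a false increase; 10 per 100,000 person-years; 21-day windows; 42-day control): 3.9%, 6.9% and 16% at *q* = 25%, 50% and 100% with 5,000,000 vaccinated, and 6.9%, 15% and 45% with 20,000,000.

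**Where there is no upward bias.**
- Skipping unrelated to the event: θ = 1.00.
- Control time proportional to each person's risk time: θ = 1.00 for 21-, 28- and 42-day windows at every *q* tried.
- Dose 2 delayed beyond the window rather than skipped, 42-day control: 1.00 for 21-day windows and 0.97 for 42-day windows at *q* = 50%.

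**Remedies that do not work.**
- Adding dose terms to the same combined layout (21-day windows, 42-day control): dose 1 gives 1.00, but dose 2 gives 1.09, 1.20 and 1.50 at *q* = 25%, 50% and 100%.
- Restricting to people with both doses: 0.95, 0.88, 0.75 and 0.50 at *q* = 10%, 25%, 50% and 100%.
- A full-length dose 1 window for 28- and 42-day outcomes: it overlaps dose 2. If dose 2 has RR 1.4 and dose 1 has none, dose 1 reads (21 + 7 × 1.4)/28 = 1.10 and (21 + 21 × 1.4)/42 = 1.20. Cutting the window at the actual dose 2 date makes its length depend on the event again.

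**The case against.** The strongest reply is that the bias needs a control interval that does not change with the number of doses, and the protocol leaves control length and timing to the SAP. Section 8.7.3.2 also speaks of control intervals in the plural, which is compatible with one per dose, and proportional control time removes the bias entirely. This stands as a limit on the finding. It does not dispose of it: the rule for combining risk time is fixed in the protocol, an outcome-specific control most naturally means one length per outcome, and nothing says that control time follows doses received.

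It can also be said that section 8.7.3.2 gives no likelihood, that section 8.3.3.3 already plans myocarditis/pericarditis analyses by dose number, and that the SCRI is a sensitivity analysis whose promotion is only possible. These points are fair and bear on severity. Subgroup results by dose would not correct the combined estimate.

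A reader might infer that the SCRI would tend to show harm from dose sequencing alone. The documents do not support that. They give no skipping share, the null RR at 25% skipping is 1.02 to 1.06 across the settings tabulated, and a delayed dose 2 does not inflate the RR. Nor should weight be put on the extreme case for myocardial infarction (208 per 100,000 person-years, 28-day window, 5,000,000 people), where two-sided rejection reaches 86%. That requires every case before dose 2 to skip it, and it reflects the large event count detecting an RR of 1.13. At 25% skipping the same calculation gives 12%, against a nominal 5%.

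**Conclusion.** The concern holds in conditional form. Combining risk time over doses received makes risk time depend on the event whenever the event stops the next dose. With control time that does not vary by dose count, the null RR then lies above 1. The size is modest: for 21-day windows and a 42-day control, about 2% to 9% at 10% to 50% skipping and 19% if every such case skips; less for 28- and 42-day windows or longer controls. These figures rest on an assumed skipping share and control length, a constant event rate, dose 2 at day 21 and truncation of dose 1 at dose 2.

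It should be corrected before the SCRI is programmed, because the analysis is the named check on exposure misclassification and may be promoted to primary.

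**What to change.** Replace the single combined risk interval in section 8.7.3.2 with dose-specific SCRI comparisons, pooled afterwards only if they are similar, as section 8.7.2.2 does for the cohort, with variance clustered on the person.

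- **Dose 1.** Include every dose 1 recipient, whether or not dose 2 followed. Use one fixed risk-window length, ended for everyone at the scheduled dose 2 day (day 21) when the outcome's window is longer. Compare it with a fixed-length control window placed after dose 2's risk window would have ended. Add a sensitivity analysis for a late dose 2 falling in that control window.
- **Doses 2 and 3.** Include only recipients who were event-free up to that dose, with fixed risk and control windows counted from it.

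With these pairs, an event before dose 2 changes nobody's risk or control time in the dose 1 comparison. For 21-day windows the expected null counts are 21:21 for each dose with a 21-day control, so the RR is 1.00.

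A simpler alternative keeps the combined interval and makes each person's control time proportional to the risk time of the doses received.

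The cost is protocol and SAP wording and a change to the SCRI cohort build, with no new data. For 28- and 42-day outcomes, dose 1 follow-up beyond day 21 is not used, and slightly fewer control days are available.

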Based on data through 12 June 2021, the Vaccine Safety Datalink (VSD) observed in analyses based on 22 cases in the risk interval, that the age- and site-adjusted rate ratio for risk of myocarditis/pericarditis in the 7 days following mRNA vaccination in individuals aged 12 to 39 years was 10.0 (95% CI, 2.9-46.5). The corresponding rate ratio for Pfizer-BioNTech original monovalent COVID-19 Vaccine was 2.4 (95% CI, 0.4-24.9). In individuals aged 12 to 39 years, the incidence rate of myocarditis/pericarditis in the 21 days following mRNA vaccination was greater in males than in females and was greater following the second dose than following the first dose (12.6 cases per million second doses vs. 4.4 cases per million first doses). Additionally, a temporal clustering of myocarditis/pericarditis occurred within the week following vaccination, with the most likely cluster occurring 0 to 5 days following vaccination. Based on these data and a benefit-risk assessment, on 23 June 2021, the ACIP concluded that the benefits of vaccinating all recommended age groups with mRNA COVID-19 vaccine clearly outweighed the risks of vaccination, including the risk of developing myocarditis after vaccination. The ACIP emphasized the need to continue monitoring outcomes of myocarditis cases after COVID-19 vaccination and that providers and the public should be informed about these myocarditis cases and the use of COVID-19 vaccines. Based on the ACIP's conclusions, COVID-19 vaccination continued to be recommended for all individuals aged ≥ 12 years under the FDA's EUA. The FDA added this safety event to the EUA factsheet, and the warnings and precautions section of prescribing information for Pfizer-BioNTech original monovalent COVID-19 Vaccine states that, "Postmarketing data demonstrate increased risks of myocarditis and pericarditis, particularly within 7 days following the second dose. The observed risk is higher among males under 40 years of age than among females and older males. The observed risk is highest in males 12 through 17 years of age" (Pfizer, 2021).

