7. RESEARCH QUESTION AND OBJECTIVES

Research questions

Among the general population, immunocompromised individuals, pregnant women, and individuals with a history of COVID-19:

- 1. What is the incidence of safety events of interest, including myocarditis/pericarditis, among individuals receiving at least 1 dose in a primary series¹ of Pfizer-BioNTech original monovalent COVID-19 Vaccine compared with that among individuals who have not received any vaccination for COVID-19 in the US?
- 2. In individuals aged 5 years and older who have received the first and second dose in a primary series¹ of Pfizer-BioNTech original monovalent COVID-19 Vaccine, what is the incidence of safety events of interest, including myocarditis/pericarditis, among individuals vaccinated with a third dose (either as an additional dose in a primary series or as a booster dose) of Pfizer-BioNTech original monovalent COVID-19 Vaccine compared with that among individuals who have not received a third dose of any COVID-19 vaccine in the US?
- 3. What is the prevalence of birth outcomes of interest (including major congenital malformations and small size for gestational age) in infants born to pregnant women who were exposed to Pfizer-BioNTech original monovalent COVID-19 Vaccine as compared with that among infants born to pregnant women who were not exposed to any COVID-19 vaccine in the US?

Primary study objectives

Among the overall study population and subgroups of pregnant women, immunocompromised individuals, and individuals with a history of COVID-19:

- 1. In individuals aged 5 years and older: To estimate the RR of safety events of interest (including myocarditis/pericarditis) following receipt of a first, second, or third (if received within 2 months of the second dose) dose in a primary series¹ of Pfizer-BioNTech original monovalent COVID-19 Vaccine compared with that among individuals with no receipt of any COVID-19 vaccine
- 2. In individuals aged 6 months through 4 years: To estimate the RR of safety events of interest (including myocarditis/pericarditis) following receipt of a first, second, or third dose in a primary series¹ of Pfizer-BioNTech original monovalent COVID-19 Vaccine compared that among individuals with no receipt of any COVID-19 vaccine

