If COVID-19 vaccines are administered without reimbursement from health insurers, there is the potential that they will not be recorded in claims and electronic health records. This situation may lead to misclassification of truly exposed individuals as "unexposed" comparators, which will underestimate vaccine coverage rates and may bias comparative risk estimates for the cohort design with concurrent unexposed comparators. The completeness of exposure data will be assessed in monitoring analyses before the final analyses are conducted by comparing study data with publicly available estimates of vaccine coverage and/or estimates based on immunization registry data from select states (if available); if the coverage estimates differ meaningfully from the "benchmarking" estimates (based on to-be-defined criteria in the SAP), then modifications to the study approach may be considered. If this happens, the SCRI may be designated as the primary study designs and/or linkage to immunization registries may be considered if feasible.

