8.7.2.2. Measures of association

For comparative analyses of general safety events, Cox models or Poisson regression will be used to estimate RRs and 95% CIs within the matched cohorts. For pregnancy outcomes, hazard ratios and 95% CIs will be estimated using Fine-Gray subdistribution proportional hazards models (using gestational age as the time scale) to account for competing risks of other end-of-pregnancy events (e.g., termination, stillbirth) (Fine JP and Gray RJ, 1999).

For comparative analysis of small size for gestational age and major congenital malformations, modified Poisson regression (Zou, 2004) will be used to estimate prevalence ratios and 95% CIs within the matched cohorts.

For the dose 1 comparative risk estimation for general safety events and pregnancy outcomes, when a second dose of vaccine is administered before the risk interval following dose 1 is complete, the risk interval will be truncated at the time of dose 2, and FU after dose 2 will be excluded from the dose 1 risk estimation. In this situation, for the dose 2 comparative risk estimation, the risk interval will start on the date of the second vaccine dose and will extend for the duration of the risk interval for dose 2.

Similarly, for dose 2 comparative risk estimation for general safety events and pregnancy outcomes, when a third dose of vaccine is administered before the risk interval following dose 2 is complete, the risk interval will be truncated at the time of dose 3, and FU after dose 3 will be excluded from the dose 2 estimation. In this situation, for the dose 3 comparative risk estimation, the risk interval will start on the date of the third vaccine dose and will extend for the duration of the risk interval for dose 3.

For comparative analysis of outcomes identified separately in dose 1, dose 2, and dose 3 cohorts, comparative risks will be estimated separately by dose number. If comparative risk estimates are similar for dose 1, dose 2, and dose 3, then data from the dose 1 exposed/dose 1 unexposed cohorts, the dose 2 exposed/dose 2 unexposed cohorts, and the dose 3 exposed/dose 3 unexposed cohorts will be combined to obtain comparative risk estimates associated with at least 1 dose of the vaccine.

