8.7.3. Sensitivity analysis

8.7.3.1. Exposure misclassification

During the early stages of the roll out of COVID-19 vaccines, many vaccinations may have occurred outside traditional medical care settings without reimbursement from health insurers. The potential for lack of recording of COVID-19 vaccines in claims and electronic health records may lead to misclassification of exposed individuals as "unexposed" individuals, which will underestimate vaccine coverage rates and bias comparative risk estimates for the cohort design with concurrent unexposed individuals as comparators. To address this potential bias in comparative risk estimates, sensitivity analysis will be performed using a SCRI design. Additional sensitivity analyses will incorporate a cohort design with historical unexposed comparators for pregnancy and birth outcomes.

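### The primary-series self-controlled analysis is specified only as one estimate over all doses, so it cannot directly check the dose-specific cohort estimates it is meant to support

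*Protocol*

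**What the plan says.** Protocol Section 8.7.3.2 sets the SCRI rule for the primary series: "the risk interval will combine person-time in the risk intervals after the first dose, after the second dose, and after the third dose", the third where applicable. The rule carries no condition. The same section leaves the choice of outcomes and the details of the control interval to the SAP, but not this rule.

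The neighbouring text treats dose differently:

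- **Objectives (Section 7).** Primary objective 1 asks for the relative risk "following receipt of a first, second, or third (if received within 2 months of the second dose) dose in a primary series". Objective 2 asks the same for ages 6 months through 4 years.
- **Cohort analysis (Section 8.7.2.2).** Here "comparative risks will be estimated separately by dose number". The step to a combined estimate opens with "If comparative risk estimates are similar for dose 1, dose 2, and dose 3".
- **Role of the SCRI.** Section 8.7.3.1, on vaccinations missing from claims, says "To address this potential bias in comparative risk estimates, sensitivity analysis will be performed using a SCRI design". Section 8.1 adds that, if exposure data prove incomplete, "the primary study design may be switched to the SCRI design". Sections 8.3.1 and 8.9 repeat that possibility.
- **Background (Section 6).** The cited surveillance result for myocarditis/pericarditis within 21 days of mRNA vaccination at ages 12 to 39 is "12.6 cases per million second doses vs. 4.4 cases per million first doses".

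**The concern.** A sensitivity analysis tests a main result only if both aim at the same quantity. For general safety events the SCRI is the only alternative design offered against exposure misclassification, since the historical-comparator cohort in Section 8.7.3.3 is confined to pregnancy and birth outcomes. Section 8.9 also relies on the SCRI against time-invariant confounding.

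The main cohort results for the primary series are one relative risk per dose. The SCRI as described yields one relative risk across doses. If it comes out below the dose 2 cohort result, three explanations are open: mixing of dose 2 with a lower-risk dose 1, exposure misclassification in the cohort, or confounding in the cohort. The planned output cannot separate the first from the other two. It could equally lie above the dose 1 cohort result for the same reason. If the SCRI were promoted to primary design without further change, the dose-by-dose part of objectives 1 and 2 would have no planned estimate for the outcomes it covers.

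**Working it through.** **1. The two rules side by side**

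| | Cohort (8.7.2.2) | SCRI, primary series (8.7.3.2) |
|---|---|---|
| Estimate by dose | Yes, first step | None named |
| Combined estimate | Only if doses are similar | Always |
| Outcomes | All general safety events | Acute onset, risk interval up to 42 days |

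Where doses differ, the protocol provides no combined cohort estimate. The SCRI and cohort results then have no quantity in common.

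**2. Illustration of the mixing**

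Inputs, from Section 6: r1 = 4.4 and r2 = 12.6 cases per million doses in 21 days. Assumption: equal person-time after doses 1 and 2.

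- Ratio of doses: 12.6 / 4.4 = 2.86.
- Pooled rate: (4.4 + 12.6) / 2 = 8.5 per million.
- Pooled relative to dose 2: 8.5 / 12.6 = 0.67.
- Pooled relative to dose 1: 8.5 / 4.4 = 1.93.

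With the same control interval for both doses, the control rate cancels in these ratios. The 67% therefore needs no background rate. It does depend on the two borrowed rates and on the equal weighting.

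**3. Precision cost of splitting by dose**

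I first reproduce the worked example in Section 8.5: 5,000,000 vaccinated, 2 doses each, 21-day window, background 10 per 100,000 person-years, true relative risk 1.4, 1:1 person-time, stated probability 92% that the upper 95% limit is below 2.5.

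- Comparator events: e0 = 5,000,000 × 2 × (21/365.25) × 10/100,000 = 57.5.
- Exposed events: e1 = 1.4 × e0 = 80.5.
- SE of the log relative risk: √(1/e0 + 1/e1) = 0.1727.
- Probability: Φ(ln(2.5/1.4)/0.1727 − 1.96) = 0.919, which matches 92%.

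With one dose per person:

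- e0 = 28.75, e1 = 40.25, SE = 0.2442.
- Probability: Φ(ln(2.5/1.4)/0.2442 − 1.96) = 0.66, the same as the 2,500,000 row of Table 9.

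This is the cohort formula, so it only indicates the loss for an SCRI, whose control interval is left to the SAP. The dose-specific cohort estimates that the protocol already plans bear the same loss.

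**The case against.** **The protocol does not forbid SCRI estimates by dose.** Section 8.3.3.3 plans myocarditis/pericarditis subgroups by dose number without limiting them to the cohort design, and Section 8.7 leaves detailed methods to the SAP, which is not shown. This stands in part: a reader might infer that dose-specific SCRI results are excluded, and the text does not go that far. But the subgroup plan is not tied to the SCRI and names one outcome, and the only SCRI rule the protocol fixes is the combined one.

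**The objectives do not fail as a whole.** A reader might infer that a switch to the SCRI would leave the primary objective unanswered. That is too strong. Research question 1 concerns receipt of at least one dose, which a combined SCRI can address. Objective 3 (third dose more than 2 months after the second) lies outside the combining rule, and the SCRI is not used for the birth outcomes of objective 4. The switch is also only a possibility, with registry linkage as an alternative, and Section 8.7 foresees an amendment for major changes to primary outcome analyses.

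**Dose number may be unreliable when the SCRI is most needed.** Section 8.3.1 expects most vaccination codes to lack dose number and may fall back on the order of recorded vaccinations. With incomplete capture, an unrecorded first dose turns a true second dose into an apparent first. This stands. It is a sound reason to keep the combined estimate and not to make the by-dose results the main SCRI result.

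**The size is borrowed.** This also stands. The cited rates are surveillance results for any mRNA vaccine at ages 12 to 39. It is tempting to divide them by the background rate in Section 8.5, but that rate is for the general population. At 10 per 100,000 person-years it would imply a dose 1 relative risk of 0.77, a sign that the two sources do not fit together. No relative risk should be quoted from them. The documents give no such dose-specific rates for the other SCRI outcomes.

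**Conclusion.** The point holds as a mismatch between two analyses in the same protocol. The primary-series SCRI, as written, gives one pooled relative risk. It cannot directly check the dose-specific cohort relative risks of objectives 1 and 2, and could not stand in for them if it became the primary design. The scope is limited to the primary series and to outcomes with risk intervals up to 42 days.

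The size is illustrative: a pooled rate about 67% of the dose 2 rate, given equal person-time after two doses and the cited rates. The documents establish that dose matters for myocarditis/pericarditis. They do not show that it matters to this extent for this vaccine in this population. The change is a cheap improvement, not a repair of a failed objective.

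**What to change.** In Section 8.7.3.2:

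1. Keep the combined primary-series estimate.
2. Add SCRI estimates by dose number, at least for myocarditis/pericarditis, using separate indicators for doses 1, 2 and, where applicable, 3 against the common control interval.
3. State that the combined estimate will be read as applying to each dose only if the dose-specific SCRI estimates meet the similarity condition of Section 8.7.2.2.
4. Note that dose-specific results need caution where dose number comes from the order of recorded vaccinations (Section 8.3.1).

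This takes a few sentences of text and no new data. The statistical cost is wider intervals per dose: on the protocol's cohort formula, the Section 8.5 example falls from 0.92 to 0.66 when only one dose per person is counted. The interpretive cost is possible misassignment of dose number. Reporting the combined estimate beside the dose-specific ones limits both.
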